Primary Objective:	The primary aim is to estimate the overall response at 12 weeks using IMWG criteria in patients with multiple myeloma when treated with immunotherapy and radiotherapy.

Secondary Objectives: The secondary aims are: 1) to estimate the median progression free survival and the median overall survival for patients treated with immunotherapy and radiotherapy, and 2) to assess the toxicity (per CTCAE version 4.0) of patients treated with immunotherapy and radiotherapy.

Exploratory Objectives: Exploratory analyses will include: 1) investigate the expression of PD-L1 and PD-L2 on myeloma plasma cells prior to and at various time points after immune checkpoint blockade and radiotherapy, 2) investigate the population of T cells (cytotoxic T cells, helper T cells and regulatory T cells) and their expression of immune checkpoint receptors (PD-1, CTLA-4, LAG3, 2B4, BTLA, TIM3, A2aR) prior to and at various time points after checkpoint blockade and radiotherapy, 3) investigate mutational burden of pre-treatment myeloma samples in the bone marrow and target site utilizing FoundationOne Heme 4) investigate the T cell receptor (TCR) repertoire in the bone marrow aspirate prior to and at various time points after immune checkpoint blockade and radiotherapy and 5) microbiome analysis prior to and after immunoradiotherapy.

Endpoints: The primary endpoint will be the overall response rate using IMWG criteria. Other end points include progression free survival and overall survival.

[figure not shown]
Table of Contents

Protocol Summary	7
SCHEMA	12
1 Study Objectives	13
1.1 Primary Objectives.....	13
1.2 Secondary Objectives.....	13
1.3 Exploratory Objectives	13
2 Background	13
2.1 Disease.....	13
2.2 Investigational Agent.....	14
2.3 Rationale.....	14
2.3.1 Overview.....	14
2.3.2 PD1/PDL1 and T-Cell Activation	14
2.3.3 Multiple Myeloma and PD1/PDL1	15
2.3.4 Abscopal Effect of Radiotherapy	16
2.3.5 Radiotherapy and Immunity.....	16
2.3.6 Harnessing the Pro-Immunogenic Effects of Radiation in Cancer Treatment: A New Paradigm.....	17
2.4 Risk/Benefit Assessment	18
2.5 Correlative Studies Background	18
2.6 Microbiome Correlative studies	21
2.6.1 To explore associations of ORR with changes in the microbiome.....	21
3 Subject Selection	23
3.1 Study Population	23
3.2 Inclusion Criteria.....	23
3.3 Exclusion Criteria	24
4 Registration Procedures	24
4.1 Patient Registration	24
5 Study Calendar	25
5.1 Schedule of Assessment	25

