2.6 Microbiome Correlative studies

2.6.1 To explore associations of ORR with changes in the microbiome.

While immune checkpoint blockade results in remarkably prolonged disease control in a subset of patients^{47,48} modulators of this phenotype are not well understood. Accumulating evidence suggests the gut microbiota play a critical role in response to both anti-PD-L1 efficacy and CTLA-4 blockade: two recently published studies by Vetizou *et al.* and Sivan *et al.* demonstrated in mouse models that the gut microbiome critically impacts response to immunotherapy^{47,48}. Remarkably, by altering the composition of commensal microbiota, the response to CTLA-4 blockade and anti-PD-L1 therapy could be manipulated and therapeutic response markedly enhanced. These pre-clinical studies provide strong rationale for our hypothesis that the human gut microbiome composition will

correlate with response to ICB and RT. Identification of commensal organisms harbored in patients with heightened antitumor immune response can ultimately be manipulated to achieve desired outcomes in a greater proportion of patients. Fecal transplant is an established clinical technique whereby microbiota can be transferred into humans to induce select therapeutic outcomes, providing direct clinical applicability of any findings ⁴⁹.

The study by Vetizou *et al.* underscores the dependence of CTLA-4 blockade on commensal microbiota ⁴⁸. First, the authors demonstrate that anti-CTLA-4 therapy is ineffective in mice that are housed in germ-free cages or treated with antibiotics.

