Taken together, the above preclinical studies lend strong support towards collection of gut microbiome samples from patients enrolling on all future immunotherapy studies. We propose to collect stool samples from study patients before treatment and at day 21, 3 months and 6 months for analysis of microbiome composition and changes after ICB and RT. Both pre-clinical and clinical data demonstrate that the addition of RT to ICB creates a robust immune response, eliciting anti-tumor immune responses in otherwise non-responding patients. Given that we expect a similar heightened response in our proposed study, our patient cohort with its expected dichotomous outcomes will be particularly suitable for microbiome analysis. The results will be an important step towards understanding, and ultimately harnessing, the interplay between the human gut microbiome and anti-tumor immune response.

Methods Stool collection will occur before treatment, at day 21, at 3 months and 6 months to

explore changes of the microbiome during ICB. Bacterial diversity and taxonomy will be estimated by high throughput sequencing (HTS) of 16S rRNA amplicons, using the MiSeq platform in the Genomic Technology Core Lab. Methods have been established in the Blaser Lab and proven to yield accurate and reproducible results.^{50,51} Analysis will be based on the QIIME (Quantitative Insights into Microbial Ecology) software package developed by the Knight lab,⁵² and machine learning analyses developed by NYU Center for Health informatics and Bioinformatics (CHIBI) investigators working on NYU Human Microbiome Program studies.^{53,54} Appendix 2 describes the protocol for stool collection.

3 Subject Selection

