5.1.2 Treatment Phase

Once eligible, patients will receive immunotherapy, nivolumab, intravenously at 240 mg every two weeks. Infusions will be given over 30 minutes (not bolus or IV push). Patients will also receive radiation of 6 Gy x 5 fractions the first week of starting immunotherapy. Immunotherapy treatment starts with the first radiotherapy fraction. Nivolumab will be given every 2 weeks. Patients will have specified laboratory values measured monthly and evaluated for response as defined by International Myeloma Working Group Criteria. Patients will continue to receive their respective immunotherapy for up to three years or until disease progression or dose limiting toxicity is reached. Patients will remain on therapy for up to 6 cycles in the setting of stable disease and for up to a year in the setting of a PR or better by 6 cycles.

5.2 Response Assessment at Week 12

Patients will have specified laboratory values measured monthly and evaluated for response as defined by International Myeloma Working Group Criteria. Patients without progression of disease as defined by IMWG criteria including assessment of plasmacytoma(s) by PET/CT will continue to receive nivolumab every 2 weeks.

5.3 Duration of Therapy and Criteria for Removal from Study:

In the absence of treatment delays due to adverse event(s), treatment may continue until one of the following criteria applies:

1. Progression of disease as defined by IMWG criteria,
2. Intercurrent illness that prevents further administration of treatment,
3. Unacceptable adverse event(s),
4. Patient decides to withdraw from the study, or
5. General or specific changes in the patient's condition render the patient unacceptable for further treatment in the judgment of the investigator.

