11.4 Analysis of Correlative Endpoints

11.4.1 Microbiome

11.5 Statistical analysis of microbiome and metagenome composition

Statistical analysis of microbiome and metagenome composition will be performed in the R statistical programming environment⁵⁶ using package *phyloseq*⁵⁷, which incorporates and builds upon community ecology packages such as *ade4* and *vegan* and employs the flexible graphic system *ggplot2*, to easily visualize complex data relationships. For 16S data, we will evaluate the adequacy of sequencing efforts using rarefaction plots. Alpha diversity index for each will be characterized through dominance, equitability, richness, evenness. The diversity metrics will be calculated at Operational Taxonomic Unit (OTU) and higher taxonomical levels to best characterize the community structure. We will test for associations of each of these alpha diversity metrics with the time relative to radiation exposure, using one-way ANOVA after even-sampling the observations to a depth cut-off maximizing the number of samples and depth. In addition, rank-abundance plots will be used to visualize differences in abundance of dominant taxa in the clinical and phenotypic groups. We will utilize skyline plots to visualize the patterns of community structure in terms of relative abundances in the collected samples between before and after the radiation treatment or between case and control samples. Similarly, for metagenomic data, skyline plots will be used to reveal functional compositions of the samples. Heat-maps will be plotted to visualize clustering patterns in the data.

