Univariate analyses. To circumvent instabilities associated with rare species, which are difficult to detect uniformly in all samples, we will focus our primary univariate analyses only on highly abundant taxa, i.e. those present at 1% or more relative abundance across all specimens. This approach will also help to reduce multiple comparison-related Type I-error inflation, which will be formally controlled by false discovery rate (FDR)⁵⁸. The differences in presence or absence of specific taxa and functional categories will be assessed by χ^2 -test at all taxonomical levels. *Paired-Sample Wilcoxon Signed Rank Test* will be used to establish the differences in relative abundance of taxa between before and after the radiation treatment or between paired samples. Depending on the dynamics observed, subsequent analyses may focus on less abundant taxa, and at higher depth, as indicated above.

Multivariate analyses. Multivariate association of the entire microbiome/metagenome with clinical and phenotypic factors will be examined with Principal Coordinate Analysis (PCoA) on Jensen-Shannon, weighted and unweighted Unifrac, and χ^2 (correspondence analysis) distances. Likewise, these distances will be used to build non-parametric multivariate Analysis of variance (ANOVA) models (ADONIS)⁵⁹ to allow for simultaneous measurement of univariate and interaction effects of the clinico-phenotypic variables on the microbiome. Starting with the microbiota and metagenomic features significantly different in univariate analyses, we will use the dimension-reduction method, canonical correlation analysis (CCA) to identify the bacteria taxa which are related radiation treatment, according to benchmarked methodologies of our prior studies^{54,60}. We will utilize a phylogenetic structure-constrained penalty function to impose phylogenetic relationships among bacteria on the model selection⁶¹.

Longitudinal analysis: We will study the evolution of microbiome over time and how that evolution is associated with the radiation treatment. The relative abundances at each taxonomical level will

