be first normalized by log-ratio transformation ⁶². Then the transformed relative abundance of each individual taxa at multiple time points will be fitted by the linear mixed model along with the time effect and all subject-specific characteristics as the independent covariates. For the nonlinear trend, we will combine the nature splines with linear mixed model in the data analysis. The same model will be applied on the indices calculated in the ecology microbial analysis. For the joint analysis of more than one taxon, we will use MCMCglmm R package to implement the multivariate generalized linear mixed model. This package gives a large flexibility in analyzing correlated multiple longitudinal response by allowing different types of covariance structure ⁶³.

12 Adverse Event Reporting Requirements

CTCAE Version 4.0 will be used for tracking the Adverse Events in this study.

Adverse event (AE) monitoring and reporting is a routine part of every clinical trial. The investigator will be required to provide appropriate information concerning any findings that suggest significant hazards, contraindications, side effects, or precautions pertinent to the safe use of the drug or device under investigation.

Safety will be monitored by evaluation of adverse events reported by patients or observed by investigators or research staff, as well as by other investigations such as clinical laboratory tests, x-rays, electrocardiographs, etc.

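### Section 11.5 ties microbiome change to radiation, which this design cannot separate from nivolumab or time, and it names no response term although response is the stated aim

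*Combined protocol and SAP*

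**What the plan says.** The aim concerns response. Section 2.6.1 is titled "To explore associations of ORR with changes in the microbiome", and section 2.6 argues that "our patient cohort with its expected dichotomous outcomes will be particularly suitable for microbiome analysis". The Protocol Summary words the exploratory objective as "microbiome analysis prior to and after immunoradiotherapy", which refers to the combination.

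Section 11.5 is built around time and radiation:

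- Alpha diversity: "We will test for associations of each of these alpha diversity metrics with the time relative to radiation exposure, using one-way ANOVA".
- Taxa: a paired Wilcoxon test before and after radiation.
- Canonical correlation analysis: taxa related to radiation.
- Longitudinal analysis: "We will study the evolution of microbiome over time and how that evolution is associated with the radiation treatment", using a mixed model with time and "all subject-specific characteristics as the independent covariates".
- Plots: samples before and after radiation, "or between case and control samples". Neither case nor control is defined.

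PCoA and ADONIS relate the whole microbiome to clinical and phenotypic variables that are not listed.

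On treatment, section 11 describes a single-arm trial and section 5.1.2 states: "Immunotherapy treatment starts with the first radiotherapy fraction". Footnote b of the section 5.1 calendar places the first fraction on Day 1, after the infusion. The calendar schedules stool before the Day 1 infusion, at the end of radiation, at C4D1 and at C7D1.

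**The concern.** There are two gaps. First, an analysis that reports taxa or trends as related to radiation needs some contrast in which radiation varies and nivolumab does not. This trial appears to have none. Second, the hypothesis concerns who responds, but the factors that 11.5 names are time and radiation. An analyst could carry out every named test, leave the response question unanswered, and publish a list of radiation-related taxa that the design cannot support. Only the exploratory microbiome conclusions are at stake. No decision rule, safety rule, or primary or secondary endpoint depends on them.

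**Working it through.** **1. Can radiation be separated from nivolumab?** The inputs are the sampling and treatment times in section 5.1. Cycle length is inferred as 28 days: infusions every two weeks fall on D1 and D15, and marrow sampling at C4D1, C7D1 and C10D1 continues every 12 weeks, so 12 weeks / 3 cycles = 4 weeks.

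| Stool sample | Radiation started | Nivolumab started | Infusions already given |
|---|---|---|---|
| Day 1, before infusion | 0 | 0 | 0 |
| End of radiation | 1 | 1 | 1 |
| C4D1 | 1 | 1 | 3 x 2 = 6 |
| C7D1 | 1 | 1 | 6 x 2 = 12 |

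With an intercept, the design has columns (1,1,1,1), (0,1,1,1) and (0,1,1,1) in every patient. Its rank is 2 for 3 parameters, so a separate radiation coefficient cannot be estimated at any number of patients. The infusion count does vary, but it is the same for all patients on schedule and is therefore tied to time. Section 6.2 allows nivolumab within 24 hours of radiotherapy, but no stool sample is scheduled in that gap. Section 2.6 gives other sampling days (before treatment, day 21, 3 months, 6 months). That is also one sample before both treatments and three after, so the result is unchanged.

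**2. Is response in the plan?** The factors that 11.5 names are time, radiation, and unlisted clinical or subject variables. Clinical response is not named. The word appears once, in the mixed-model paragraph, where it means the model's outcome variable. By contrast, section 2.5 (Aim 3) does name a test of mutational burden against response, a Spearman correlation. Response entered only as a main effect in the mixed model would still not address association with *change*. That needs a response-by-time term.

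**3. How much could a response contrast detect?** The microbiome plan states no sample size or power, so the inputs come from section 11.1: 26 evaluable patients and response rates of 20% (null) and 40% (alternative). The two-stage rule (continue with at least 4/13, reject with at least 10/26) reproduces: exact power at 40% is 0.606 (stated 60%) and exact one-sided type I error is 0.021 (stated 0.025).

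- Responders: 0.20 x 26 = 5.2 and 0.40 x 26 = 10.4, so about 5 to 10.
- Early stop: P(X <= 3) with X ~ Bin(13, p) is 0.747 at p = 0.20 and 0.169 at p = 0.40. Thirteen patients is a realistic final size.
- Detectable difference d for responders versus non-responders (one metric, two-sided 0.05, 80% power): two-sample noncentral t with df = n1 + n2 - 2 and noncentrality d / sqrt(1/n1 + 1/n2).

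| Responders / non-responders | sqrt(1/n1 + 1/n2) | d at alpha 0.05 | d at alpha 0.0025 |
|---|---|---|---|
| 10 / 16 | 0.403 | 1.18 SD | 1.72 SD |
| 5 / 21 | 0.498 | 1.45 SD | 2.13 SD |
| 3 / 10 (most responders possible at a stage-1 stop) | 0.658 | 2.03 SD | 3.22 SD |

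The last column assumes about 20 taxa with a Bonferroni-like correction (0.05 / 20 = 0.0025). The plan uses FDR and gives no taxon count.

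**4. Who still has samples?** C4D1 is day 3 x 28 + 1 = 85, inside the week-12 window of 84 +/- 7 days. C7D1 is day 6 x 28 + 1 = 169, about 12 weeks later. Section 5.3 ends treatment at progression, and section 5.1.2 limits stable disease to 6 cycles. If those rules are followed, C7D1 samples come mainly from responders, and change at C7D1 partly reflects who remains. Section 5.1.2 also gives a three-year limit. The two statements need reconciling, and this review takes no position between them.

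**The case against.** The strongest reply is that a reader might infer from 11.5 that the plan never tests its aim, and the documents do not go that far. PCoA and ADONIS take unspecified clinical and phenotypic variables with interactions, the mixed model takes all subject characteristics, rank-abundance plots compare clinical groups, and section 2.6 mentions machine-learning analyses next to its remark on dichotomous outcomes. Response fits into any of these. This stands: the gap is that response is not specified, not that it is excluded.

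A reader might also infer that every before/after comparison in 11.5 makes a causal claim about radiation. It need not. In the ANOVA and Wilcoxon sentences radiation can serve as a time marker, and other sections speak of change after, or during, checkpoint blockade. The canonical correlation sentence and the opening longitudinal sentence do link change to radiation, and for those the reply fails.

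The case/control phrase may mean responder versus non-responder, so it should be defined or deleted rather than assumed empty. The responder count is also not what limits covariates in the mixed model. Abundance is the outcome there, so the limit on between-patient covariates is about 26 patients.

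Finally, the aim is exploratory, it is listed fifth in the Protocol Summary and is absent from section 1.3, and FDR control is planned. That keeps the point minor but does not answer it.

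**Conclusion.** The non-identifiability holds in full. It follows from the single arm, the common start and the sampling schedule, and it does not depend on sample size or on the inferred cycle length. Section 11.5 can describe change after the start of combined treatment. It cannot assign that change to radiation.

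The mismatch with the aim holds as a failure to specify: response is the stated interest, yet no analysis names it and no response-by-time term is given. The stronger statement, that the aim goes untested, is not supported because the open-ended variables could include response.

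Nor do the figures show that even one response contrast is comfortably powered. Detectable differences are about 1.2 to 1.5 SD with 10 to 5 responders of 26, and about 2 SD or more after a stage-1 stop, for one unadjusted metric. These figures assume a response rate of 20% to 40%, complete samples and a normal-theory comparison, so they are an optimistic guide. This is a minor but worthwhile correction to an exploratory section.

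**What to change.** Edit section 11.5:

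1. Replace references to radiation treatment with the start of combined nivolumab and radiotherapy, in line with the Protocol Summary, and state that no radiation-specific conclusion will be drawn.
2. Name week-12 IMWG response as the factor of interest and rank the contrasts. The main contrast is a response-by-time term in the mixed model using samples up to C4D1. Baseline composition by response in ADONIS is supportive. C7D1 is descriptive because of selective dropout. Patients who progress before C4D1 may also lack that sample, so report the number of samples by response at each time.
3. Define the case and control groups (for example, as responders and non-responders) or delete the phrase.
4. Replace the open list of subject characteristics with one or two covariates named in advance, since there will be about 26 patients, or 13 if the trial stops at stage 1.

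The cost is a text amendment. The stool and response data are already scheduled. The downsides are fewer adjustment variables and a response contrast of low precision, so the results should be reported as exploratory estimates with intervals.

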1. Changing personnel : Replacing Research Nurse [name] with [name]
2. Changing personnel: Data Manager (Myeloma team): [name]
3. Section 3.3 - Exclusion criteria #12 - Prior exposure to immune checkpoint inhibitor
4. Correcting Nivolumab infusion from 60 mintues to 30 minutes as per BMS and FDA treatment prescriptions.
5. Clarifying stool collection timepoints : Baseline, end of radiation, C4D1 and C7D1
6. saliva collection added to the calendar for C1D1 (before infusion)
7. Adding investigator : [name]
8. Updated Appendix 2 : for stool collection timepoints.
9. Clarifying radiation given as 5 fractions and removing “consecutive days” language.
10. Removing immune monitoring blood samples from section 8.1, 14.2 and 14.5.
11. Revising bone marrow aspiration to 20ml.

Informed consent changes :

1. Clarifying that patients will receive 5 fractions of radiation treatment.

Protocol Summary

Full Title:	Radiotherapy and Immunotherapy for Systemic Effect in Myeloma (RISE-M) Trial
Short Title:	RISE-M Trial
Clinical Phase:	II
Principal Investigator:	[name], MD
Sample Size:	N = 30
Accrual Ceiling:	This study will enroll 30 subjects and screen up to 50.
Study Population:	Eligible patients will have multiple myeloma.
Accrual Period:	2 years
Study Design:	Eligible patients have multiple myeloma with measurable disease in the blood and a targetable soft tissue or bony lesion with radiotherapy. All eligible patients will receive immunotherapy (Nivolumab) plus radiotherapy, 6 Gy x 5 fractions, to a targetable lesion. Immunotherapy treatment starts with the first radiotherapy fraction. Nivolumab will be given every 2 weeks. Patients will have specified laboratory values measured bi-monthly and evaluated for response at 12 weeks as defined by International Myeloma Working Group Criteria. Patients will continue to receive their respective immunotherapy until disease progression or dose limiting toxicity is reached.
Study Duration:	Patients will have approximately 25-30 visits and a follow up for up to 3 years.
Study Agent/Intervention:	Patients with multiple myeloma will receive Nivolumab intravenously at 240 mg every two weeks. Infusions will be given over 30 minutes (not bolus or IV push). Patients will continue to receive infusions every two weeks until disease progression or dose limiting toxicity is reached. Patients will receive 5 fractions of radiation. A dose of 6 Gy x 5 days will be administered.

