11.1 Sample Size/Accrual Rate

As mentioned, a Simon's two-stage optimal design [Simon, 1989] will be used. The null hypothesis that the true response rate is 20% will be tested against a one-sided alternative. If there are 3 or fewer responses in these 13 patients, the study will be stopped. Otherwise 13 additional patients will be accrued for a total of 26 patients. The null hypothesis will be rejected if 10 or more responses are observed in 26 patients. This design yields a one-sided type I error of 0.025 and power of 60% when the true response rate is 40%. The target sample size is 26 evaluable patients and up to 30 patients (4 extra patients) will be accrued to account for non-evaluable patients or patients who withdraw prior to evaluation.

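### The per-taxon longitudinal models in section 11.5 adjust for an open-ended set of patient characteristics in 13 to 30 patients, and false-discovery control is not stated to cover them

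*Combined protocol and SAP*

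**What the plan says.** Section 11.5 has three labelled parts: univariate, multivariate and longitudinal.

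In the longitudinal part, relative abundances at every taxonomic level are log-ratio transformed. Each taxon is then "fitted by the linear mixed model along with the time effect and all subject-specific characteristics as the independent covariates". The same model is used for the ecological indices, splines are added where the trend is not linear, and joint models are fitted for several taxa. No covariate list, cap or selection rule is given. The one penalised method in section 11.5 belongs to the canonical correlation analysis in the multivariate part.

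Multiplicity is addressed once, in the univariate part, after the restriction to taxa at 1% relative abundance or more: "This approach will also help to reduce multiple comparison-related Type I-error inflation, which will be formally controlled by false discovery rate (FDR"). No level is named. The longitudinal part mentions neither the filter nor any error control.

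The number of patients is set in section 11.1: "The target sample size is 26 evaluable patients and up to 30 patients (4 extra patients) will be accrued". On the interim rule it says: "If there are 3 or fewer responses in these 13 patients, the study will be stopped". Stool is collected four times per patient (section 5.1 footnote d, section 8.4, Appendix 2). The Protocol Summary lists the microbiome work among the exploratory objectives.

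**The concern.** The coefficient of a fixed patient characteristic is estimated from differences between patients. Four samples per patient do not turn 30 patients into 120 for that purpose. A rule that puts every characteristic into every model therefore draws on 13 to 30 independent units, while the trial collects many baseline variables. Followed as written, it gives imprecise patient-level effects. If it is trimmed until the model fits, the choice of covariates falls to the analyst after the data are seen.

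The second issue is the number of models: one per taxon, at each taxonomic level, plus the diversity indices. Without a stated error-control family, some apparent changes over time would be expected by chance. Section 2.6.1 presents microbiome findings as something that could be carried into the clinic, so a false taxon signal would not be harmless.

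**Working it through.** **Sample size figures.** The documents give no power or error rate for the microbiome models; the number of patients comes from the two-stage design. With a stop at 3 or fewer of 13 and rejection at 10 or more of 26, P(reject) = sum over x = 4 to 13 of P(X = x | 13, p) × P(Y ≥ 10 − x | 13, p).

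- p = 0.40: 0.606, against the stated power of 60%.
- p = 0.20: 0.021, under the stated one-sided 0.025, which fits as a ceiling.

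The probability of stopping with 13 evaluable patients is P(X ≤ 3 | 13, p):

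- p = 0.20: 0.0550 + 0.1787 + 0.2680 + 0.2457 = 0.747.
- p = 0.40: 0.169.

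So 13, 26 and 30 patients are all realistic.

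**Precision of patient-level effects.** Let N be the number of patients and p the number of fixed patient-level parameters besides the intercept. Residual between-patient degrees of freedom (df) are N − 1 − p. For independent normal covariates that explain nothing further, the expected variance of one coefficient is proportional to 1/(N − p − 2). The standard error relative to a one-covariate model is therefore √[(N − 3)/(N − p − 2)].

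| N | p | Residual df | Standard error ratio |
|---|---|---|---|
| 30 | 3 | 26 | √(27/25) = 1.04 |
| 30 | 5 | 24 | √(27/23) = 1.08 |
| 30 | 10 | 19 | √(27/18) = 1.22 |
| 30 | 20 | 9 | √(27/8) = 1.84 |
| 26 | 3 | 22 | √(23/21) = 1.05 |
| 26 | 5 | 20 | √(23/19) = 1.10 |
| 26 | 10 | 15 | √(23/14) = 1.28 |
| 26 | 20 | 5 | √(23/4) = 2.40 |
| 13 | 3 | 9 | √(10/8) = 1.12 |
| 13 | 5 | 7 | √(10/6) = 1.29 |
| 13 | 10 | 2 | √(10/1) = 3.16 |

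Residual df reach zero at p = 29 for N = 30, p = 25 for N = 26 and p = 12 for N = 13. One parameter more makes the fixed effects rank-deficient.

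**Time effect.** With four complete visits and a random intercept, the time slope is estimated from each patient's deviations from that patient's own mean. Fixed patient-level covariates cancel from those deviations. In a simulation built on this decomposition (N = 30, 4,000 replicates, p from 1 to 28), the type I error for time was 0.043 to 0.054 and the mean standard error stayed at 0.081 to 0.082.

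**Multiplicity.** The documents give neither the number of taxa nor a per-taxon threshold. Assuming m independent tests at 5% without correction, P(at least one false positive) = 1 − 0.95^m:

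- m = 10: 40%.
- m = 20: 64%, with 20 × 0.05 = 1 false positive expected.
- m = 50: 92%, with 2.5 expected.
- m = 100: 99%, with 5 expected.

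**The case against.** Three stronger readings are tempting, and the documents do not support them as statements of fact.

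*That the models cannot be estimated.* Section 11.5 does not count the covariates. A reader can reach 29 from what is collected: PD-L1 and PD-L2 (2), eight T-cell subsets, seven checkpoint receptors and mutational burden at two sites make 19. ECOG, weight, magnesium, uric acid, LDH, TSH and beta-2 microglobulin make 26. Serum M-protein, urine M-protein and free light chain make 29. But the first 19 are readouts of other exploratory aims, and nothing says that they enter the microbiome models. Many of the others are measured repeatedly; entered as time-varying terms they also use within-patient information, and the N − 1 − p limit no longer applies as stated. Failure to fit follows only if the rule is taken literally, with that many fixed baseline terms.

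*That the longitudinal results as a whole are unstable.* The stated aim is change over time, and with complete data and fixed covariates the time effect is untouched. The reservation is that complete data are doubtful: the last stool sample is at C7D1, while section 5.1.2 limits patients with stable disease to six cycles and ends treatment at progression. Missing samples, time-varying covariates, interactions with time or splines could weaken this result.

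*That the tests are uncorrected at 5%.* This is inferred from silence. A one-taxon model could be read as univariate and so covered by the false-discovery sentence, and the 1% filter, if carried over, would reduce the number of tests. The text says neither, and its separate headings point the other way.

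What stands is an unlimited covariate rule in a small trial, and a false-discovery family that is not stated to include these models.

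**Conclusion.** The point holds in a limited form. The covariate rule overfits the patient-level effects: the standard error is about 1.2 times that of a one-covariate model with 10 fixed covariates at N = 30, 1.8 times with 20, and 3.2 times with 10 at N = 13. These ratios assume fixed, mutually independent covariates; correlated ones would do worse. How far along that scale the analysis falls depends on a covariate count that the plan does not give.

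Error control for the longitudinal per-taxon models and the diversity indices is not stated. The 64% and 92% figures for 20 and 50 taxa show what is at stake only under independence and uncorrected 5% tests, both of which are assumptions. The 13-patient case should not be presented as the expected one: its probability is 0.747 at a 20% response rate but 0.169 at 40%.

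Priority is low. The analysis is exploratory, and no decision rule in sections 11.1 or 11.3.1 uses it.

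**What to change.** Two changes of wording in section 11.5.

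1. In the longitudinal part, replace the open-ended covariate phrase with a random patient intercept, time, and a short named list of patient-level covariates fixed before sequencing data are seen. For example, allow no more than 3 to 5 parameters at 26 to 30 patients, and fewer if the trial stops at 13. The exact number is a judgement: 3 to 5 parameters cost 4% to 8% in standard error at N = 30 and 5% to 10% at N = 26. Describe the remaining characteristics without modelling them.

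2. State that Benjamini-Hochberg control, at a named level, also applies to the time effect across taxa within each taxonomic level in the longitudinal models, and across the set of diversity indices. Say whether the 1% abundance filter applies there too.

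The cost is SAP text only, with no change to data collection or sample size. The downside is fewer nominally significant exploratory results and fewer adjusted baseline effects to report.
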